5.4.1 Durvalumab Dose Modification

Dose reductions for durvalumab are not permitted. For dose modification and toxicity management guidelines for durvalumab, refer to Appendix G.

5.4.2 *Olaparib dose levels*

Dose Level	Olaparib
Level 0	300 mg BID
Level -1	250 mg BID
Level -2	200 mg BID
Level -3	Discontinue

Subjects requiring more than two dose reductions will have to discontinue olaparib. 100 mg and 150 mg tablets will be supplied for olaparib.

5.4.3 *Toxicities that require discontinuation from study treatment*

Protocol therapy should be discontinued if a subject experiences:

- Any CTCAE Grade 4 toxicity with the exception of:
 - CTCAE Grade 4 neutropenia of 5 days or fewer duration
 - CTCAE Grade 4 nausea/vomiting or diarrhea that resolves to Grade 3 or less within 72 hours
 - CTCAE Grade 4 laboratory abnormalities that can be readily corrected with 72 hours and do not result in hospitalization.
- CTCAE Grade 3 thrombocytopenia with hemorrhage
- CTCAE Grade 3 febrile neutropenia
- Hy's Law (AST or ALT >3x ULN with concomitant serum bilirubin >2x ULN and no alternate etiology)
- Bone marrow findings consistent with myelodysplastic syndrome (MDS)/acute myeloid leukemia (AML)

5.5 **Concomitant Medications and Supportive Care**

Because of the potential for drug-drug interaction, the concurrent use of all other drugs, over-the-counter medications, and alternative therapies must be documented on the eCRF.

Subjects should not donate blood while participating in this study or for at least 90 days following the last infusion of durvalumab or olaparib.

Refer to Appendix D for more information on concomitant medications and supportive care guidance.

5.6 **Other Concomitant Treatment**

Any medications, with the exceptions noted in Appendix D, which are considered necessary for the subject's welfare, and which it is believed will not interfere with the study medication, may be given at the discretion of the Investigator, providing the medications, the doses, dates and reasons for administration are recorded in the EDC.

In addition, any diagnostic, therapeutic or surgical procedure performed during the study period must be recorded in the EDC.

All medications (prescriptions or over-the-counter medications) continued at the start of the trial (from the time of informed consent) or started during the study or until 30 days from the end of the last protocol treatment and different from the study medication must be documented.

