APPENDIX H. DOSE MODIFICATION AND TOXICITY MANAGEMENT GUIDELINES FOR OLAPARIB

Olaparib dose reductions based on hematologic nadir

Granulocytes and Platelets	Olaparib Dose Adjustment
ANC < LLN* but \geq 1000/mm3 and/or PLT < LLN but \geq 50,000/mm3 (CTCAE Grade 1-2)	Investigator judgment to continue study treatment in full dose or if dose interruption, this should be for a maximum of 4 weeks; appropriate supportive treatment and causality investigation
ANC < 1000/mm3 and/or PLT < 50,000/mm3 (CTCAE Grade 3 - 4)	Hold olaparib. Once toxicity resolves to Grade 1, olaparib may be continued -1 dose level.

*LLN = lower limit of normal

- If the ANC nadir is under 1000/mm3 (CTCAE Grade 3 - 4) and/or the platelet nadir is under 50,000/mm3 (CTCAE Grade 3 - 4) after a 1 dose level reduction of olaparib, then the next cycle will be started at -2 dose level once toxicity resolved to CTCAE Grade 1 or better
- Subjects requiring more than two dose reductions will discontinue olaparib

Management of toxicity related to olaparib

Any toxicity observed during the course of the study could be managed by interruption and/ or dose reduction of the dose if deemed appropriate by the Investigator. Olaparib must be interrupted until the subject recovers completely or the toxicity reverts to the NCI-CTCAE Grade 1 or less. If olaparib is delayed more than 8 weeks for any reason, or if a dose reduction below 200 mg daily is required, subjects will discontinue treatment with olaparib.

- Where toxicity reoccurs following re-challenge with olaparib, and where further dose interruptions are considered inadequate for management of toxicity, then the subject should be considered for dose reduction or must permanently discontinue treatment with olaparib.
- Treatment must be interrupted if any NCI-CTCAE Grade 3 or Grade 4 AE occurs which the Investigator considers to be related to administration of olaparib.

Adverse Event with Possible Relationship to Olaparib	Action to Take

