Neutropenia and leukopenia	CTC Grade 3 or worse neutropenia occurs	
Manage as deemed appropriate by the investigator with close follow up and interruption of study drug. Primary prophylaxis with Granulocyte colony-stimulating factor (G-CSF) is not recommended, however, if a subject develops febrile neutropenia, study treatment should be stopped and appropriate management including G-CSF should be given according to local hospital guidelines. Please note that G-CSF should not be used within at least 24 h of the last dose of study treatment.
 
Study treatment can be restarted at the same dose if an AE of neutropenia or leukopenia have been recovered up to CTC AE Grade less than or equal to Grade 1 (ANC > 1.5 x 10⁹/L). Growth factor support should be stopped at least 24h before restarting study drug (7 days for pegylated G-CSF).
 
Any subsequent interruptions will require study treatment dose reductions to 250 mg BID as a first step and to 200 mg

		BID as a second step for a 300 mg monotherapy starting dose
Thrombocytopenia	CTCAE Grade 3 or worse	
Study treatment should be interrupted for a maximum of 4 weeks. In some cases, management of thrombocytopenia may require platelet transfusions. Platelet transfusions should be done according to local hospital guidelines.
 
Any subsequent interruptions will require study treatment dose reductions to 250 mg BID as a first step and to 200 mg BID as a second step for a 300 mg monotherapy starting dose

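### Appendix H names two different olaparib doses for the first restart after uncomplicated Grade 3 (or brief Grade 4) neutropenia, and nothing says which governs

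*Combined protocol and SAP*

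**What the plan says.** Section 5.4.2 sets the olaparib levels: 300 mg BID (level 0), 250 mg BID (level -1), 200 mg BID (level -2), then discontinuation. More than two reductions means stopping olaparib. Section 5.4 refers sites to Appendix H as a whole for managing toxicity.

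Appendix H then covers low neutrophil counts twice.

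- **Hematologic nadir table.** For an ANC below 1000/mm3, labelled Grade 3-4: "Hold olaparib. Once toxicity resolves to Grade 1, olaparib may be continued -1 dose level". A bullet beneath it covers a repeat nadir after one reduction: "then the next cycle will be started at -2 dose level once toxicity resolved to CTCAE Grade 1 or better".
- **Neutropenia and leukopenia row of the toxicity table.** For Grade 3 or worse neutropenia: "Manage as deemed appropriate by the investigator with close follow up and interruption of study drug". Then: "Study treatment can be restarted at the same dose if an AE of neutropenia or leukopenia" has recovered to Grade 1 or less. Then: "Any subsequent interruptions will require study treatment dose reductions to 250 mg BID as a first step", with 200 mg BID as the second step. The row ties these steps to a 300 mg starting dose given as monotherapy.

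The general text of Appendix H adds that any toxicity "could be managed by interruption and/ or dose reduction of the dose if deemed appropriate by the Investigator".

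Section 5.4.3 limits the cases concerned. It stops protocol therapy for Grade 3 febrile neutropenia and for Grade 4 toxicity, but exempts "CTCAE Grade 4 neutropenia of 5 days or fewer duration".

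**The concern.** The two texts share a trigger and a recovery condition but attach different doses to the first restart. Two sites could treat the same event, restart at different doses, and both be following Appendix H.

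What is at stake is re-exposure to a marrow-suppressive drug just after a marrow toxicity, and consistent dosing across a multi-center trial. Section 9.2.2 has monitors review whether treatment followed the protocol, and section 10.4.4 has dose modifications summarized. A monitor reading Appendix H cannot say which restart dose was correct.

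**Working it through.** The plan states no figure to reproduce, so the check sets the two texts side by side and walks the section 5.4.2 dose levels under each.

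**1. Is it the same event?** The nadir table uses ANC < 1000/mm3. The neutropenia row uses Grade 3 or worse neutropenia. The prolonged-hematological-toxicity row of the same appendix equates Grade 3 or worse neutropenia with ANC < 1 x 10^9/L. Since 1 L = 10^6 mm3, 10^9/L ÷ 10^6 = 1000/mm3. The triggers are identical.

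**2. Is it the same recovery?** The nadir table requires resolution to Grade 1, and the neutropenia row requires Grade 1 or less. For the restart decision these are the same, and both texts call for a hold first.

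**3. Which cases remain after section 5.4.3?** Febrile neutropenia and Grade 4 neutropenia lasting more than 5 days stop protocol therapy. Uncomplicated Grade 3, and Grade 4 of 5 days or fewer, remain.

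**4. Dose sequence from 300 mg BID**, taking the named dose at each step and applying the two-reduction cap:

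| Neutropenia event | Nadir table | Neutropenia row |
|---|---|---|
| 1st | 250 mg BID | 300 mg BID |
| 2nd | 200 mg BID | 250 mg BID |
| 3rd | stop | 200 mg BID |
| 4th | – | stop |

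The sequences stay one event apart throughout.

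**5. Size at the first restart.** Nadir table: 2 x 250 = 500 mg/day. Neutropenia row: 2 x 300 = 600 mg/day. Difference: 600 - 500 = 100 mg/day; 100/600 = 16.7% of full dose.

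**6. Does any text choose?** Section 5.4 cites Appendix H without an order. Section 5.4.2 gives the levels and the cap only. The nadir table is not a general rule that a more specific row would displace: it concerns dose reductions for blood counts and gives its own ANC threshold. The rest of Appendix H points both ways:

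- Grade 3 or worse anemia restarts at a reduced dose, and Grade 3 or higher general non-hematologic toxicity drops one level. These match the nadir table.
- The re-challenge bullet ("Where toxicity reoccurs following re-challenge with olaparib, and where further dose interruptions are considered inadequate for management of toxicity") considers reduction on recurrence, which matches the neutropenia row.

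**The case against.** The strongest reply is that the two texts can be read together. One says olaparib may continue a level down and the other says it can restart at the same dose. Both permit and neither orders, and Appendix H leaves management to the investigator. On this reading the first reduction is optional and becomes mandatory at the next interruption. The -2 bullet applies only after a reduction has been made, so it does not force the first one.

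Much of this stands. The plan does not issue two incompatible commands for the first restart, and a reader who inferred that would be going beyond the text. But if both doses are allowed, the site's choice also decides which sequence the subject follows, and the later steps are worded as requirements. A second event then leads to 200 mg BID on one sequence and 250 mg BID on the other. Discretion can justify either dose for one subject, but it does not say where the first reduction is meant to fall. The statement that guidance is not a mandate is in Appendix G, on immune-mediated events, and does not cover Appendix H.

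It is also fair to say that the risk is small. Both texts require a hold and recovery, both doses are protocol levels, and section 5.4.3 removes the worst cases. Section 1.2.5 lists anemia as the only hematologic toxicity expected in 20% or more of subjects. That suggests neutropenia is less frequent, though it gives no rate.

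Two stronger readings are tempting, and the documents do not support them:

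- **A subject already at 250 mg BID for another toxicity.** A reader might infer a second conflict, 200 mg BID under the -2 bullet against 250 mg BID under the neutropenia row. That requires the row to count interruptions only for neutropenia. Its wording is any subsequent interruption. If the earlier interruption counts, the row also requires a reduction and the difference may vanish.
- **Thrombocytopenia.** The row's wording on subsequent interruptions might suggest a full-dose first restart, against level -1 in the nadir table for platelets below 50,000/mm3. But the row states no first-restart dose, and the nadir table can fill that gap. The mismatch is implied, not stated.

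**Conclusion.** The plan is wrong as written, and the point is minor. For a first uncomplicated Grade 3 neutropenia at 300 mg BID, or Grade 4 of 5 days or fewer, Appendix H names both 250 and 300 mg BID as the restart dose and sets no precedence. The difference is 100 mg/day, 16.7% of full dose, and the sequences remain one event apart.

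The first-restart comparison rests only on the section 5.4.2 levels and on the subject being at the starting dose. The longer sequences also assume that each event is an uncomplicated neutropenia of this kind, that no reductions occur for other toxicities, and that sites take the named dose at each step. The documents give no incidence of Grade 3-4 neutropenia, so the number affected is unknown and could be zero.

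A reader might infer that uneven olaparib exposure weakens the efficacy result. The documents give no basis for that: the 32-subject design, the eight-success rule and the toxicity stopping boundaries do not depend on the restart dose.

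**What to change.** State one rule. The default should be the nadir table's, which is the more cautious and matches the anemia and general non-hematologic rows.

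1. **Neutropenia row, restart dose.** For Grade 3 or worse neutropenia, replace the same-dose sentence with: *restart one dose level below the dose at onset, per the hematologic nadir table, once ANC recovers to Grade 1 or less.*
2. **Neutropenia row, later steps.** Keep any subsequent interruption as the trigger, because narrowing it to Grade 3 or worse events would loosen an existing safeguard. Change the steps to: *require a further one-level reduction; a subject needing more than two dose reductions discontinues olaparib (5.4.2).* Delete the closing reference to a monotherapy starting dose, since olaparib is given here with durvalumab.
3. **Thrombocytopenia row.** Add only a cross-reference to the nadir table for the first restart, and align the step wording with item 2.

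If the sponsor and drug supplier prefer a same-dose first restart, amend the Grade 3-4 row of the nadir table instead. That row also covers platelets, so the amendment should say whether the change applies to them.

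The cost is a text correction to Appendix H and one memo to sites, with no extra subjects, visits or tests.

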APPENDIX D: MEDICATIONS WITH THE POTENTIAL FOR DRUG-DRUG INTERACTIONS

Olaparib is an investigational drug for which no data on in vivo interactions are currently available. Based on in vitro data and clinical exposure data, olaparib is considered unlikely to cause clinically significant drug interactions through inhibition or induction of cytochrome P450 enzyme activity. In vitro data have, however, also shown that the principal enzyme responsible for the formation of the 3 main metabolites of olaparib is CYP3A4 and consequently, to ensure subject safety, the following potent inhibitors of CYP3A4 must not be used during this study for any subject receiving olaparib.

While this is not an exhaustive list, it covers the known potent inhibitors, which have most often previously been reported to be associated with clinically significant drug interactions.

Prohibited Concomitant Medications while subjects are taking Olaparib:

Agent	Agent
ketoconazole	rifapentine
itraconazole	rifabutin
ritonavir	carbamazepine
indinavir	phenobarbitone
saquinavir	nevirapine
telithromycin	modafinil
clarithromycin	St John's Wort (Hypericum perforatum)
nelfinavir	
phenytoin	
rifampicin	

After enrollment if the use of any potent inducers or inhibitors of CYP3A4 are considered necessary for the subject's safety and welfare, the Sponsor Principal Investigator must contact the AstraZeneca Study Physician. A decision to allow the subject to continue in the study will be made on a case-by-case basis.

If there is no suitable alternative concomitant medication then the dose of olaparib should be reduced for the period of concomitant administration. The dose reduction of olaparib should be recorded in the CRF with the reason documented as concomitant CYP3A inhibitor use.

- Strong CYP3A inhibitors – reduce the dose of olaparib to 100mg BID for the duration of concomitant therapy with the strong inhibitor and for 5 half-lives afterwards.
- Moderate CYP3A inhibitors - reduce the dose of olaparib to 150mg BID for the duration of concomitant therapy with the moderate inhibitor and for 3 half-lives afterwards.
- After the washout of the inhibitor is complete, the olaparib dose can be re-escalated.

Strong or Moderate CYP3A inducers

Strong (e.g., phenobarbital, phenytoin, rifampicin, rifabutin, rifapentine, carbamazepine, nevirapine, enzalutamide and St John's Wort) and moderate CYP3A inducers (e.g. bosentan, efavirenz, modafinil) of CYP3A should not be taken with olaparib.

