Non-hematologic toxicities including nausea, vomiting, and diarrhea	Grade 1 and Grade 2 If subjects develop intolerable Grade 1 or Grade 2 toxicities (per subject) then they can undergo a dose reduction. For Grade 4 toxicities despite optimal medical therapy, hold olaparib until equal or under Grade 1. Resume at one dose level reduction. Events of nausea and vomiting are known to be associated with olaparib treatment. In study, they are generally mild to moderate (CTCAE Grade 1 or Grade 2) severity, intermittent and manageable on continued treatment. The first onset generally occurs in the first month of treatment with the incidence of nausea and vomiting not showing an increase over the treatment cycles.

		No routine prophylactic anti-emetic treatment is required at the start of study treatment; however, subjects should receive appropriate anti-emetic treatment at the first onset of nausea or vomiting and as required thereafter, in accordance with local treatment practice guidelines
General non-hematologic toxicities excluding nausea, vomiting, and diarrhea	Grade 3 or higher toxicities	Delay until recovery to Grade 1 or lower and reduce one dose level to 250mg BID). A maximum of 2 dose reductions can be made for repeat toxicity.
Anemia	CTCAE Grade 1 or Grade 2 (Hemoglobin (Hb) > 8 g/dl)	Investigate and manage as deemed appropriate by the investigator with or without interruption of study drug or change in dose, taking into account previous history of anemia. Common treatable causes of anemia (e.g., iron, vitamin B12 or folate deficiencies and hypothyroidism) should be excluded. In some cases, management of anemia may require blood transfusions.
	CTCAE Grade 3 (Hb < 8g/dl) or worse	
Study treatment should be interrupted for up to maximum of 4 weeks to allow for bone marrow recovery and the subject should be managed appropriately. Study treatment can be restarted at the reduced dose if Hb has recovered to > 10 g/dl. Any subsequently required anemia related interruptions, considered likely to be dose related, or coexistent with newly developed neutropenia, and or thrombocytopenia, will require a further study treatment dose reduction to 200 mg BID.
 
If a subject has been treated for anemia with multiple blood transfusions without study treatment interruptions and becomes blood transfusion dependant as judged by investigator, study treatment should be permanently discontinued.

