Renal Impairment	Creatinine clearance below threshold for study inclusion (51ml/min)	
If subsequent to study entry and while still on study therapy, a subject's estimated CrCl falls below the threshold for study inclusion (≥51 ml/min), retesting should be performed promptly.
 
A dose reduction is recommended for subjects who develop moderate renal impairment (calculated creatinine clearance by Cockcroft-Gault equation of between 31 and

		
50 ml/min) for any reason during the course of the study: the dose of olaparib should be reduced to 200 mg BID.
 
Because the CrCl determination is only an estimate of renal function, in instances where the CrCl falls to between 31 and 50 mL/min, the investigator should use his or her discretion in determining whether a dose change or discontinuation of therapy is warranted.
 
Olaparib has not been studied in subjects with severe renal impairment (creatinine clearance \leq 30 ml/min) or end-stage renal disease; if subjects develop severe impairment or end stage disease is it recommended that olaparib be discontinued.

--	--	--

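### Appendix H sets the olaparib toxicity dose floor at 200 mg a day, half the 400 mg a day floor in Section 5.4.2; after a one-step renal reduction only the 5.4.2 table forces a stop

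*Combined protocol and SAP*

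**What the plan says.** Section 5.4 sends sites to Appendices G and H for toxicity management. Section 5.4.2 then lists the olaparib levels: 300, 250 and 200 mg BID as levels 0, -1 and -2, with discontinuation as level -3. It adds a count rule: "Subjects requiring more than two dose reductions will have to discontinue olaparib". Appendix H repeats that count rule.

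Appendix H, under management of olaparib toxicity, leaves interruption or dose reduction to the investigator's judgment. It then gives a dose limit in milligrams per day: "if a dose reduction below 200 mg daily is required, subjects will discontinue treatment with olaparib".

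Three other provisions bear on the point:

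- **Renal row, Appendix H.** For a man whose creatinine clearance falls to 31-50 mL/min "for any reason during the course of the study: the dose of olaparib should be reduced to 200 mg BID". The row also lets the investigator decide whether a dose change or discontinuation is warranted.
- **Toxicity rows, Appendix H.** The general non-hematologic row says "A maximum of 2 dose reductions can be made for repeat toxicity". After a first interruption, the neutropenia and thrombocytopenia rows call for "study treatment dose reductions to 250 mg BID as a first step", with 200 mg BID as the second step.
- **Appendix D.** With a strong CYP3A inhibitor, sites are to "reduce the dose of olaparib to 100mg BID for the duration of concomitant therapy with the strong inhibitor"; with a moderate one, to "reduce the dose of olaparib to 150mg BID for the duration of concomitant therapy with the moderate inhibitor". These doses are temporary: "After the washout of the inhibitor is complete, the olaparib dose can be re-escalated".

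**The concern.** Two current sections give different floors for the same drug and the same purpose, and the lower figure is in the appendix that sites are told to use. The text does not say whether the daily figure is a slip for 200 mg BID or a true daily total.

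What is at stake is consistent dosing. Consider a man on the renal dose of 200 mg BID who later has a toxicity that calls for a lower dose. A site working from 5.4.2 stops olaparib. A site working only from Appendix H finds that neither its dose floor nor its reduction count requires that. The case can arise, because entry requires a clearance of at least 51 mL/min (Section 3.1.9), just above the band in which the renal row applies. Section 6.2 reports no olaparib data below 50 mL/min.

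**Working it through.** **Inputs.** Starting dose 300 mg BID, stated as 600 mg in total per day (Section 5). Levels, count rule and tablet strengths of 100 and 150 mg (Section 5.4.2). Floor, count rule and renal row (Appendix H). Temporary doses (Appendix D).

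**Daily doses.** Daily dose = 2 × BID dose.

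- Level 0: 2 × 300 = 600 mg/day, which reproduces the stated total.
- Level -1: 2 × 250 = 500 mg/day.
- Level -2: 2 × 200 = 400 mg/day; 400/600 = 67% of the starting dose.
- Appendix H floor: 200 mg/day; 200/600 = 33% of the starting dose.
- Ratio of the two floors: 400/200 = 2.

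**Doses between the two floors.** The supplied tablets can make 150 mg BID (300 mg/day, 50% of the start) and 100 mg BID (200 mg/day, 33%). Both are below 400 mg/day. Neither is below 200 mg/day, since 100 mg BID equals that figure. They serve here only to test the rules; no toxicity row offers either dose.

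**Each route against the three rules.** The last step in each route is a further cut to 150 mg BID; a cut to 100 mg BID gives the same answers.

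| Route (mg BID) | Reductions | Count above 2 stops? | Appendix H floor stops? | 5.4.2 table stops? |
|---|---|---|---|---|
| 300 → 250 → 200 → 150, by toxicity steps | 3 | Yes | No | Yes |
| 300 → 250, renal cut to 200, → 150 | 3 | Yes | No | Yes |
| 300, renal cut to 200, → 150 | 2 | No | No | Yes |

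The floors diverge in effect only in the last row, where the level table is the only one of the three rules that ends olaparib.

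**Do the toxicity rows settle it?** Only in part. The rows that name 250 mg BID as the first reduced dose do not fit a man already on 200 mg BID. The rows worded as a reduction of one dose level do point to discontinuation, but only when read with the 5.4.2 table.

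**Effect on a correction.** Changing the floor to 200 mg BID with no exception would conflict with Appendix D, since 200 and 300 mg/day are both below 400 mg/day.

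**The case against.** The strongest reply is that 5.4.2 already answers the question. It defines levels by dose, not by the number of cuts, so a man on 200 mg BID is at level -2 however he got there. Several Appendix H rows speak of dose levels, and the only definition of those is in 5.4.2. The Appendix H floor is a condition for stopping, so a site that stops earlier under 5.4.2 breaks neither rule. All of this stands. It makes the problem a conflict between sections and not a missing rule. It does not make the Appendix H figure right.

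The reply also disposes of three stronger inferences that a reader might draw.

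- **That Appendix H permits 100-150 mg BID for toxicity.** It does not. It merely fails to require a stop at those doses; they are named only in Appendix D, for drug interactions.
- **That the daily floor is the only stop in Appendix H.** It is not. Appendix H also stops olaparib for more than two reductions, a delay beyond 8 weeks, transfusion dependence, MDS/AML and confirmed pneumonitis, and recommends stopping for severe renal impairment.
- **That a renal cut falls outside the toxicity limits because it is not for toxicity.** The documents do not support this. The renal row applies whatever the cause, which can include drug-related injury, and it sits in the table of events possibly related to olaparib. The gap does not depend on this reading, because the general count allows two reductions for any cause.

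**Conclusion.** The conflict is real and minor. The Appendix H toxicity floor is half the one in 5.4.2 (200 against 400 mg/day). The count rule makes the difference harmless on the stepwise route. After a single renal cut from 300 to 200 mg BID, neither the Appendix H floor nor the count forces a stop at the next cut, and the 5.4.2 table alone does.

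The documents do not say how many of the 32 men could be affected. The case needs a fall in clearance to 31-50 mL/min while still on 300 mg BID, a renal reduction that is partly discretionary, a later toxicity calling for a lower dose, and a site that does not apply 5.4.2. The number is therefore likely to be small. The primary endpoint, sample size and exact binomial test do not depend on which floor applies.

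The conclusion assumes that both sections are meant to be operative and that 5.4.2 states the intended levels. That the daily figure is a slip is plausible but not shown.

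**What to change.** In Appendix H, under management of olaparib toxicity, replace the 200 mg daily floor with: 'below 200 mg BID (level -2, Section 5.4.2), except temporary Appendix D reductions for CYP3A inhibitors'.

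Optionally, add to the renal row: '200 mg BID is level -2 however it is reached; a toxicity that requires a dose below 200 mg BID means discontinuation, while interruption and restart at 200 mg BID where this Appendix allows it (including the anemia row) is not a further reduction.' The last clause is needed because the anemia row names 200 mg BID as the dose after a further reduction, which a man on the renal dose already takes.

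The cost is one phrase and, if wanted, one sentence, with no new visit, procedure or analysis. The downside is that a few men who might have continued below 200 mg BID would stop olaparib, which 5.4.2 already requires.

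### Two rows of Appendix H restart olaparib after Grade 4 events for which Section 5.4.3 ends protocol therapy, and the protocol does not say which governs

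*Combined protocol and SAP*

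**What the plan says.** Section 5.4.3 of the protocol lists the toxicities that end treatment. It opens "Protocol therapy should be discontinued if a subject experiences" and puts any Grade 4 toxicity first, with three exceptions:

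- Grade 4 neutropenia lasting no more than 5 days;
- "CTCAE Grade 4 nausea/vomiting or diarrhea that resolves to Grade 3 or less within 72 hours";
- Grade 4 laboratory abnormalities readily corrected within 72 hours and not leading to hospitalization.

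Appendix H gives the olaparib instructions for events possibly related to that drug. Two rows matter here:

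- Nausea, vomiting and diarrhea: "For Grade 4 toxicities despite optimal medical therapy, hold olaparib until equal or under Grade 1", followed by an instruction to resume at one dose level lower.
- General non-hematologic toxicity other than those three, Grade 3 or higher: "Delay until recovery to Grade 1 or lower and reduce one dose level to 250mg BID".

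Section 5.4 refers the reader to Appendices G and H for managing toxicities and gives no order of precedence. The sentence saying that the text is guidance and not a mandate stands in Appendix G, about immune-mediated events. Appendix H has the word guidelines in its title but no such sentence.

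**The concern.** The two places give opposite instructions for the same event. Under 5.4.3 the subject stops. Under Appendix H the subject waits for recovery and restarts olaparib at a lower dose. In a multi-center trial, two sites could each follow the protocol as written and treat the same Grade 4 toxicity differently, one of them re-exposing the subject to the drug. What is at stake is subject safety and consistent conduct between sites. No efficacy analysis is affected.

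**Working it through.** **Side-by-side reading.** The question for each row is whether a 5.4.3 exception could cover the Grade 4 event.

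| Grade 4 event | Section 5.4.3 | Appendix H | Result |
|---|---|---|---|
| Non-hematologic, non-laboratory, not nausea/vomiting/diarrhea | No exception: discontinue | Delay to Grade 1 or lower, reduce to 250 mg BID | Direct conflict |
| Nausea/vomiting or diarrhea, down to Grade 3 or less within 72 h | Exempt | Hold to Grade 1 or lower, resume one level lower | Compatible |
| Nausea/vomiting or diarrhea, still Grade 4 after 72 h | Discontinue | Hold to Grade 1 or lower, resume one level lower | Conflict |

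*Worked case.* A subject on 300 mg BID has Grade 4 vomiting for four days. Four days is 96 hours, which exceeds 72, so the exception is not met and 5.4.3 ends therapy. Appendix H holds olaparib until Grade 1 or lower and restarts one level down, at 250 mg BID in the Section 5.4.2 table.

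*Does single-agent continuation reconcile them?* Section 5.4 lets a subject who stops one drug for an adverse event continue on the other. That would keep durvalumab after an olaparib toxicity. It does not explain restarting olaparib itself.

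*Does another part of the protocol show the intent?* Appendix G's table for non-immune reactions discontinues at Grade 4, with judgment allowed for laboratory values. That agrees broadly with 5.4.3 and leaves the two Appendix H rows as the exception.

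**Check of the toxicity boundary in Section 10.2.** Inputs from the protocol: stop at 4 events in 8 subjects, 5 in 16, 7 in 24 or 9 in 32; true rates 0.15 and 0.35. Method: exact binomial recursion. At each look, add Binomial(8, p) events to the distribution of subjects' event totals that have not yet crossed, record the probability at or above the boundary, remove it and continue.

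- p = 0.15: 0.0214 + 0.0627 + 0.0190 + 0.0092 = 0.1123 (stated 0.11).
- p = 0.35: 0.2936 + 0.4232 + 0.1155 + 0.0599 = 0.8922 (stated 0.89).

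Both stated figures are correct.

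**Sensitivity, on an assumed share.** Suppose a share f of all boundary events went uncounted because the subject was restarted. The counted rate is p(1 − f). The documents give no f. At p = 0.35:

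| f | Counted rate | Probability of stopping |
|---|---|---|
| 0.01 | 0.35 × 0.99 = 0.3465 | 0.885 |
| 0.05 | 0.35 × 0.95 = 0.3325 | 0.852 |
| 0.10 | 0.35 × 0.90 = 0.3150 | 0.802 |

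**The case against.** The strongest reply is that the texts are complementary: 5.4.3 decides who stops, and Appendix H doses those who do not. The heading of 5.4.3 speaks of toxicities that require discontinuation, it sits in the body of the protocol, and Appendix H is titled as guidelines. For nausea, vomiting and diarrhea this reading is tenable, because 5.4.3 exempts the short-lived events and does not say how to dose afterwards. But the row carries no time limit, so the reader has to supply one. For the general non-hematologic row the reading fails: 5.4.3 leaves no non-laboratory Grade 4 event of that kind to be dosed. Nor do the documents state that the body prevails, and the operative verb in 5.4.3 is itself only that therapy should be discontinued.

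Safeguards also exist. Appendix H requires interruption for any related Grade 3 or 4 event, and discontinuation after more than two reductions or a delay beyond 8 weeks. Section 5.7 removes a subject whom the physician judges it dangerous to retreat. SAE reporting and twice-yearly data and safety monitoring committee review continue. These reduce the risk without resolving the contradiction.

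A reader might infer three stronger points. The documents do not support them.

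- *The hematologic rows conflict as well.* Their wording is permissive. For anemia, "Study treatment can be restarted at the reduced dose if Hb has recovered to" the stated level; for neutropenia, "Study treatment can be restarted at the same dose if an AE of neutropenia or leukopenia have been recovered". Some of these events will meet an exception, and permission to restart can be read subject to 5.4.3.
- *Febrile neutropenia is restarted.* Section 5.4.3 lists "CTCAE Grade 3 febrile neutropenia" as a reason to discontinue, and Appendix H says treatment is stopped for it, in contrast to interruption for other neutropenia. The later line "Growth factor support should be stopped at least 24h before restarting study drug" can apply to non-febrile cases.
- *The toxicity stopping rule is compromised.* Section 10.2 counts a non-immune event if it requires trial discontinuation, which can be read as a property of the event, whatever a site did next. The term is undefined, but any loss rests on an assumed share. Only non-immune events are exposed, and Appendix H describes olaparib nausea and vomiting as generally mild to moderate, so a low share is more plausible.

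**Conclusion.** The conflict is real in two Appendix H rows: direct for general non-hematologic toxicity, and present for nausea, vomiting and diarrhea once Grade 4 persists past 72 hours. It rests on the text alone and needs no assumption about event rates. It should be corrected, because following Appendix H as written could re-expose a subject after an event for which 5.4.3 ends therapy. How often this would happen cannot be derived from the documents.

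The boundary figures of 0.11 and 0.89 stand. If 1% to 5% of boundary events were left uncounted, which is an assumption, the probability of stopping at a true rate of 0.35 would move from 0.892 to between 0.885 and 0.852. What trial discontinuation means in Section 10.2 is a secondary matter for the sponsor to clarify. Sample size, power and the primary test are unaffected.

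**What to change.** 1. Head Appendix H with: *Section 5.4.3 takes precedence; hold-and-restart instructions apply to Grade 4 events only when a 5.4.3 exception is met.* This line also covers the hematologic rows and febrile neutropenia without further edits.
2. In the general non-hematologic row, limit the delay-and-reduce instruction to Grade 3 and add: *Grade 4: discontinue per 5.4.3 unless an exception is met.*
3. In the nausea, vomiting and diarrhea row, add: *Grade 4 not falling to Grade 3 or less within 72 hours: discontinue per 5.4.3.*

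The cost is one heading line and two row edits. A few subjects who might have tolerated a reduced dose will stop, as 5.4.3 already requires. If the sponsor intends the Appendix H approach, it should amend 5.4.3 instead; either way the two must agree. Appendix G's Grade 4 row favors keeping 5.4.3.

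A rule counting every 5.4.3 event toward the Section 10.2 boundary is not part of this fix. It could enlarge the counted event while the boundary stays at 4, 5, 7 and 9. If the counted rate rose from 0.15 to an assumed 0.165, the same recursion puts the probability of stopping at 0.158 instead of 0.112; at 0.18 it is 0.213.
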